### **8.2.4 Adverse/Medical Events and Serious Adverse Events**

All adverse/medical events encountered during the study will be reported on the source documents and the eCRF, and will be carefully monitored and assessed with respect to seriousness, severity, and relationship to the study or study drug. Adverse/medical events will be followed until the event is resolved, condition stabilizes (for conditions with long recovery period or those that progressed to chronic form) or the event is otherwise explained or the patient is lost to follow-up. It is the responsibility of the Investigator to ensure that adequate medical care is provided to patients during the study. All SAEs occurring within 30 days following the completion/discontinuation of the study must be reported to the Sponsor regardless of the suspected drug/event causal relationship. SAEs for which the Investigator suspects a causal relationship to the study drug must be reported to the Sponsor irrespective of the time elapsed since the last dose of the study drug.

#### **8.2.4.1 Definition of Medical/Adverse Events**

**Medical Event:** Any new untoward medical occurrence or worsening of a pre-existing condition in a patient that occurs after signing the ICF but before receiving an investigational product.

**Adverse Event:** An AE is any untoward medical occurrence in a clinical investigation in a patient administered a pharmaceutical or other therapeutic product, not necessarily

having a causal relationship with this treatment. An AE can therefore be any unfavourable and unintended sign, symptom or disease temporally associated with the use of a product, whether or not considered related to that product.

An AE does include:

- exacerbation of a pre-existing illness. This includes acute episodes/crisis of a chronic underlying condition.
- an increase in frequency or intensity of a pre-existing episodic event or condition
- a condition detected or diagnosed after study treatment administration, even though it may have been present prior to the start of the study
- a continuous persistent disease or symptom present at baseline that worsens following the start of the study

An AE does not include:

- a pre-existing disease or condition present or detected at the start of the study that does not worsen
- surgical procedures that had been planned prior to enrolment into the study
- the disease or disorder being studied, or a sign or symptom associated with the disease or disorder, unless it has worsened
- an overdose of either the study treatment or concurrent medication without any signs of symptoms

#### 8.2.4.2 Adverse/Medical Event Considerations

Note that the definition of AEs/MEs could include accidents (e.g., motor vehicle accidents) and the reasons for changes in concomitant medication (drug and/or dose), medical, nursing and/or pharmacy consultation, admission to hospital and surgical operations, and the worsening of a pre-existing medical condition.

Planned hospital admissions and/or surgical operations/procedures for an illness or disease that existed before the investigational product was given or the patient was enrolled in a clinical trial are not to be considered AEs/MEs.

If a patient's dosage is reduced or treatment is discontinued as a result of an AE, study site personnel must clearly document the circumstances and data leading to any such dosage reduction or discontinuation of treatment.

Prior to enrolment, study site personnel will note the occurrence and nature of each patient's medical condition(s) in the source documents and the appropriate section of the eCRF. During the study, site personnel will again note any change in the condition(s) and the occurrence and nature of any AEs/MEs.

Abnormal laboratory findings (e.g., clinical chemistry, hematology, urinalysis), 12-lead ECG abnormalities or other abnormal assessments (e.g. vital signs) which are not part of a larger medical condition which is already recorded as an adverse event and which are judged by the Investigator to be clinically significant must be recorded as AEs or SAEs if they meet the definition of an AE as defined in [Section 8.2.4.1](#) or SAE as defined in [Section 8.2.4.6](#). The Investigator should exercise his or her medical and scientific

judgement in deciding whether an abnormal laboratory finding or other abnormal assessment is clinically significant.

#### 8.2.4.3 Procedures for Adverse/Medical Event Monitoring and Recording

MEs will be collected from the time the ICF is signed, and AEs will be collected from the time the treatment starts. The AEs and SAEs related to the underlying condition will be recorded separately.

Patients will be instructed to report AEs/MEs to the Investigator. Reports of adverse events will be elicited using a verbal probe and recorded in the source documentation and on the Adverse Event page of the eCRF. The Investigator or delegate should always ask the same open-ended and non-leading verbal questions of the patient to inquire about AE/ME occurrence. Appropriate questions include:

“How are you feeling?” or “How do you feel?” or for pediatric patients, “How does your child seem to feel?”

“Have you had any (other) medical problems since your last visit/assessment?” or “Have you felt any different in any way since starting the new medication/treatment or since your last visit/assessment?” or for pediatric patients, “Has your child had any (other) medical problem or seemed to act differently in any way since his/her last visit/assessment?”

“Have you taken any new medicines, other than those provided in this study, since your last visit/assessment?” or for pediatric patients, “Has your child needed to take any medicines, other than those provided in this study, since his/her last visit/assessment?”

Based on the patient’s response to these questions, the Investigator should ask additional questions relevant to the specific complaint, such as:

- How severe is/was the symptom?
- How often did the symptom occur?
- How long did the symptom last?

All AEs/MEs will be recorded and evaluated by the Investigator for their seriousness, severity, and relationship to the investigational product or study.

The Investigator should attempt to establish a diagnosis of the AE based on signs, symptoms, and/or other clinical information. Wherever possible, a diagnosis should be documented rather than the individual signs/symptoms.

The Investigator must also question the patient about any previously reported AEs that have not resolved.

The Investigator will then rate the intensity, seriousness, and causality of the AEs and will also document any measures taken to address the AE. Causality should be rated in terms of relationship to the study medication as follows: not related, possibly related, probably related, definitely related. See [Section 8.2.4.4](#) for further definitions of

relationship to study medication. All of this information should be clearly recorded in the source documents.

The Investigator should employ this probe at each assessment. AEs will be collected throughout the study.

All AEs must be followed until resolution, until the condition stabilizes, until the event is otherwise explained, or until the patient is lost to follow-up. The Investigator is responsible to ensure that follow-up includes any supplemental investigations as may be indicated to elucidate as completely as practical the nature and/or causality of the AE. This may include additional laboratory tests or investigations, histopathological examinations, or consultation with other health care professionals.

#### 8.2.4.4 Causality

The relationship of an adverse event to study drug should be determined by the Investigator after thorough consideration of all facts that are available. Assessment of causality is based on considering associative connections (time or place), pharmacological explanations, previous knowledge of the drug, presence of characteristic clinical or pathological phenomena, exclusion of other causes, and/or absence of alternative explanations. The causal relationship of an adverse event to study drug will be assessed according to the following criteria (based on World Health Organization definitions):

Not related: Temporal relationship to study drug administration is missing or implausible, or there is no evident cause.

Possibly related: Reasonable time sequence to administration of study drug, but event could also be explained by concurrent disease or other drugs or chemicals - information on drug withdrawal could also be lacking.

Probably related: Reasonable time sequence to administration of study drug, but unlikely to be attributed to concurrent disease or other drugs or chemicals, and which follows a clinically reasonable response on withdrawal (de-challenge). Re-challenge information is not required.

Definitely related: Plausible time relationship to study drug administration; event cannot be explained by concurrent disease or other drugs or chemicals. The response to withdrawal of the drug (de-challenge) should be clinically plausible. The event must be definitive pharmacologically or phenomenologically, using a satisfactory rechallenge procedure if necessary.

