#### 8.2.4.7 Procedures for Serious Adverse Event Reporting

Patients will be instructed to report SAEs to the Investigator immediately (**within 24 hours**) by telephone. The Investigator must report all SAEs to the Sponsor **within 24 hours** of occurrence or notification by the patient. These events must be faxed to the Sponsor using the Sponsor’s standard SAE form. The Sponsor will provide a list of project contacts for SAE receipt, fax numbers and telephone numbers.

The Investigator will always provide an assessment of causality at the time of the initial report.

A follow-up SAE form must be completed by the responsible Investigator/delegate and faxed to the Sponsor **within 5 calendar days**. Furthermore, as additional relevant follow-up information becomes available, the Investigator must complete a follow-up SAE form and fax it to the Sponsor.

The Sponsor will submit serious adverse drug events to the appropriate regulatory agencies, in line with local regulatory requirements and timelines.

Investigators must also report all SAEs to their respective IRB/IEC responsible for the study. The Sponsor will promptly inform all other sites of SAEs occurring at a single site that are at least possibly related to the study medication and are unexpected. All site Investigators will report these events to their IRB/IEC following the same timelines as above or following local IRB/IEC policy, whichever takes precedence.

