#### Adverse Events

A summary table of adverse events will include the following information:

- number of patients exposed to study treatment,
- number of patients experiencing at least one AE,
- number of patients experiencing at least one severe AE,
- number of patients experiencing at least one serious AE,
- number of patients experiencing at least one drug-related AE,
- number of deaths,
- total number of patients withdrawn (and reason for withdrawal) and
- number of withdrawals due to an AE.

All adverse experiences will be coded using MedDRA. Adverse events will be defined as: 1) AEs that occurred or worsened (increased in severity and/or frequency) on or after the first dose of study medication. 2) AEs with a missing start date and a stop date on or after the first dose of study medication. 3) AEs with both a missing start and stop date. AEs will be summarized by treatment and by MedDRA system organ class (SOC) and Preferred Term. SAEs that occurred within 14 days after treatment discontinuation will be considered treatment-emergent AEs. Serious adverse events that occurred within 30 days after treatment discontinuation will be included in the database.

Adverse events will be summarized by treatment group using the total number of AEs, the total number and percent of patients who experience an AE, and the number and percent of patients who experienced an AE within each SOC (and preferred term within an SOC). AEs will also be presented by severity (mild, moderate, severe), by seriousness (serious, non-serious) and by relationship to study medication (at least possibly related, not related). The number of patients withdrawn will also be presented.

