8.1 Adverse Events

A summary table of adverse events will include the following information:

- number of patients exposed to study treatment
- number of patients experiencing at least one AE
- number of patients experiencing at least one severe AE
- number of patients experiencing at least one serious AE
- number of patients experiencing at least one drug-related AE
- number of deaths
- total number of patients withdrawn (and reason for withdrawal)
- number of withdrawals due to an AE

Adverse events will be coded using MedDRA. Adverse events are defined as AEs that occurred or worsened (increased in severity and/or frequency) on or after the first dose of study medication. Serious adverse events (SAEs) that occurred within 14 days after treatment discontinuation will be considered to be SAEs. Serious adverse events that occurred within 30 days after treatment discontinuation will be included in the database.

Adverse events will be summarized by treatment group using the total number of AEs and total exposure to the treatment, the total number and percent of patients who experience an AE, and the number and percent of patients who experienced an AE within each SOC (and preferred term within an SOC). AEs will also be presented by severity (mild, moderate, severe), by seriousness (serious, non-serious) and by relationship to study medication (at least possibly related, not related). The number of patients withdrawn will also be presented.

To count the number of patients who experienced each AE, patients who experienced the same AE multiple times will only be counted once for the corresponding preferred term. Similarly, if a patient experiences multiple AEs within the same SOC, that patient will be counted only once for that SOC. AEs will be tabulated presenting the SOC alphabetically, and within each SOC, preferred terms will be presented in decreasing order of the total number of patients who experienced each AE. In summaries presenting the

incidence of AEs by severity, seriousness, and relation to study medication, a patient with multiple events coded to a given preferred term or SOC will be counted once for that preferred term or SOC according to the most severe event, the most serious event, or the event with the closest relationship to study medication.

A listing of serious adverse events and a listing of withdrawals due to AEs will be presented. Patient deaths will be listed separately and discussed with patient narratives.

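### Protocol 8.2.4.4 contradicts itself: 'not related' takes in events with no evident cause, while the rest of the section counts the absence of another cause towards the drug

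*Protocol*

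**What the plan says.** Protocol 8.2.4.3 has the investigator rate every AE on a four-level scale and refers to 8.2.4.4 for the definitions. The lowest level reads: "Not related: Temporal relationship to study drug administration is missing or implausible, or there is no evident cause".

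The introduction to 8.2.4.4 names the considerations that bear on causality, among them "exclusion of other causes, and/or absence of alternative explanations". The other three levels are:

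- 'Possibly related' is worded as: "Reasonable time sequence to administration of study drug, but event could also be explained by concurrent disease or other drugs or chemicals". The definition adds that the response to stopping the drug may be unknown.
- 'Probably related': reasonable timing, other causes unlikely, and a reasonable response when the drug is withdrawn.
- 'Definitely related': plausible timing, "event cannot be explained by concurrent disease or other drugs or chemicals", a plausible response to withdrawal, and a definitive pharmacological or phenomenological picture.

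The rating is used downstream. SAP 8.1 lists the "number of patients experiencing at least one drug-related AE" in its summary table, and both it and Protocol 11.4.1.4 split AEs into at least possibly related and not related. SAP 14.3.1 plans tables of adverse drug reactions, serious adverse drug reactions and AEs by causality. Under Protocol 8.2.4.7 the sponsor informs other sites of SAEs that are "at least possibly related to the study medication and are unexpected". The SAP does not redefine the categories.

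**The concern.** When an event follows dosing at a plausible interval and nothing else explains it, the missing alternative normally counts as evidence for the drug. The section's introduction and its upper two categories follow that reasoning. The second limb of 'not related' turns the same observation into a reason to exclude the drug.

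This is the operative rule for raters. If it is followed literally, unexplained events fall on the not-related side of every investigator-rated split. Newly seen, unexplained events are the most exposed, and these are the ones that cross-site notification is meant to pick up. The trial is also open-label (Protocol 3.1), so an unclear rule is applied with the arm known.

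**Working it through.** No arithmetic applies: the documents give no figure on this point and no input from which to estimate how many events would be misrated. The check is to take one kind of event through the four definitions and then follow the rating into the outputs.

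**Test event:** plausible timing, no alternative explanation found, no information yet on what happens when the drug is withdrawn.

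| Category in 8.2.4.4 | What it requires | Does the test event meet it? |
|---|---|---|
| Not related | Timing missing or implausible, OR no evident cause | Yes on its wording, through the second limb |
| Possibly related | Reasonable timing and a competing explanation | No: there is no competing explanation |
| Probably related | Other causes unlikely and a reasonable response to withdrawal | Not yet: the response is unknown |
| Definitely related | No other explanation, plausible response to withdrawal, definitive picture | Not yet: the response is unknown |

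'Possibly related' does tolerate missing withdrawal information, but only for an event that something else could explain. The test event therefore clearly meets only 'not related'.

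If a response to withdrawal later becomes known and is positive, the same event can meet 'probably' or even 'definitely' while still meeting the second limb of 'not related'. The categories are then not mutually exclusive, and the text does not say which prevails.

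**Is the test event realistic?** Yes. Protocol 8.2.4.7 requires SAEs to reach the sponsor within 24 hours, with a causality assessment in the initial report. The response to withdrawal may not be known by then.

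**Where the rating goes:**

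| Output | Depends on relatedness? | Safeguard in the documents |
|---|---|---|
| Table 14.3.1.1, related-AE row | Yes | Footnote: worse of investigator and company ratings |
| Table 14.3.1.8, AEs by causality | Yes | Column headed as worst case |
| Tables 14.3.1.4, 14.3.1.5 and 14.3.1.7, adverse drug reactions and serious adverse drug reactions | Yes | None stated: the shells only refer back to Table 14.3.1.2 |
| Notification of other sites (Protocol 8.2.4.7) | Yes | Text does not say whose rating decides |
| All-causality AE and SAE tables | No | Not needed |
| SAE reporting to the sponsor up to 30 days (Protocol 8.2.4) | No | Not needed |

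The body of SAP 8.1 does not state the worst-case rule, and neither document gives the definitions that the company uses for its own rating.

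**Direction:** the second limb can only add events to 'not related'. Where it has an effect, it lowers the related counts.

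**The case against.** The strongest reply is that the clause is ambiguous, not reversed. The definitions are introduced as criteria for the causal relationship of an event to study drug, so no evident cause may have been meant as no evident causal link to the drug. On that reading the contradiction disappears. The reading is possible, and no document shows that any rater applied the literal one. But the text does not say it, and each of the other three categories is defined by whether another cause could explain the event. A rater has no textual reason to prefer the charitable reading, so the wording defect stands.

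The objections to a large impact carry more weight. Three stronger conclusions that a reader might draw are not supported:

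- *Every relatedness table under-counts.* Tables 14.3.1.1 and 14.3.1.8 use the worse of two ratings, so a company rating can recover an event that the investigator rated not related. Under-counting is possible, not established. Nor is relatedness among the safety endpoints in Protocol 11.2.3, which cover AEs and SAEs regardless of cause, discontinuations, laboratory tests and ECG.
- *Safety alerts are blocked.* All SAEs within 30 days reach the sponsor whatever the suspected cause, and investigators report all SAEs to their ethics committee. The cross-site rule does not say that the investigator's rating alone decides. Notification may be affected; no more can be said.
- *Deferiprone neutropenia would be hidden.* Protocol 9.1 does say that the cause is currently unknown. But 8.2.4.4 also tells raters to weigh previous knowledge of the drug, the protocol presents agranulocytosis as the most significant SAE associated with deferiprone, and neutropenia is defined and managed by neutrophil count in 8.2.4.9. It is a weak example; a new, unexpected event is the better one.

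The obvious rewrite, 'another evident cause', also has a problem. It would overlap with 'possibly related', could move disease-explained events down to 'not related', and would leave the test event without a category.

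**Conclusion.** The section is wrong as written. Absence of another cause counts towards the drug in its introduction and upper categories, and against it in 'not related'. A well-timed, unexplained event without de-challenge information clearly fits only 'not related'.

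The size is unknown. The direction is towards fewer investigator-rated drug-related AEs, adverse drug reactions and serious adverse drug reactions, with a possible effect on notification of unexpected SAEs to other sites. The conclusion about direction assumes that raters follow the literal text. How much of the effect survives in the tables depends on how often the company rating differs and whether the worst-case rule covers the adverse drug reaction tables; the SAP settles neither. The point deserves correction because the wording can give a wrong rating and is cheap to repair, not because a bias in the results has been shown.

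**What to change.** 1. In Protocol 8.2.4.4, replace the second limb with wording such as: *or the event is clearly explained by another cause, so that a contribution of study drug is unlikely*. This stays distinct from 'possibly related', where another cause could also explain the event.
2. State that a well-timed event with no alternative explanation and no de-challenge information is rated at least possibly related, and extend the 'possibly related' definition to admit it.
3. State in SAP 8.1 that the worse of the investigator and company ratings, both made under these definitions, applies to Tables 14.3.1.1, 14.3.1.4, 14.3.1.5, 14.3.1.7 and 14.3.1.8.
4. Before the final analysis, have the company check SAEs rated 'not related' that have plausible timing and no recorded alternative cause, by the same rule in both arms.

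The cost is a small wording change, a short SAP addition and a limited review. SAP 3.2 projects 213 patients to have completed or withdrawn, with 17 still on treatment and enrolment on hold. New wording would therefore reach few future ratings, and most of the work is the retrospective check in step 4. Because the trial is open-label, the criteria for that check should be fixed in writing before it starts. Treatment, visits and the efficacy analysis do not change.
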